**Table JPCS.7.2. Best Overall Response When Confirmation of Responses Required for Part C**

Overall Response First Time Point (1)	Overall Response Subsequent Time Period	Confirmed Best Overall Response
CR	CR ( $\geq$ 28 days from 1)	CR
CR	CR (<28 days from 1)	SD
CR	PR	SD
CR	MR	SD
PR	$\geq$ PR ( $\geq$ 28 days from 1)	PR
PR	$\geq$ PR (<28 days from 1)	SD
PR	MR	SD
MR	$\geq$ MR ( $\geq$ 28 days from 1)	MR
MR	$\geq$ MR (<28 days from 1)	SD
CR/PR/MR	SD	SD
CR/PR/MR	PD	SD if minimum duration of stable disease is met a , otherwise PD

Overall Response First Time Point (I)	Overall Response Subsequent Time Period	Confirmed Best Overall Response
CR/PR/MR	NE/Missing	SD if minimum duration of stable disease is met a , otherwise NE

Abbreviations: CR = complete response; MR = minor response; NE = not evaluable; PD = progressive disease; PR = partial response; SD = stable disease.

a CR/PR/MR occurs at study day >35.

### 7.3.2. Secondary Efficacy Endpoints

#### 7.3.2.1. Parts A and B

The study was not designed to make an efficacy assessment in Parts A and B, the following are the key secondary endpoints to consider for the 2 parts.

**BOR:** BOR is defined per RECIST version 1.1 using investigator-assessed time point responses. All time point responses observed while on study treatment and during short-term follow-up, but before the initiation of post-discontinuation therapy, will be included in the derivation. Responses will require confirmation (based on RECIST version 1.1), but where appropriate BOR and endpoints using BOR may also consider unconfirmed responses.

**ORR:** The ORR is the percentage of patients with a best response of CR or PR.

**DoR:** The DoR is defined only for responders (patients with a CR or PR). It is measured from the date of first evidence of a CR or PR to the date of objective progression or the date of death due to any cause, whichever is earlier.

**DCR:** The DCR is the percentage of patients with a best response of CR, PR, or SD.

**CBR:** The CBR is the percentage of patients with a best response of CR or PR, or SD for at least 6 months.

#### 7.3.2.2. Part C

**BOR:** defined per INRC (Park et al. 2017). Details are provided in Protocol Section 9.4.6.2.1. All time point responses observed while on study treatment and during short-term follow-up, but before the initiation of post-discontinuation therapy, will be included in the derivation. Responses will require confirmation ([Table JPCS.7.2](#)), but where appropriate BOR and endpoints using BOR may also consider unconfirmed responses (for example, interim analysis).

**DoR:** defined only for responders (patients with a CR or MR or PR). It is measured from the date of first evidence of a CR or MR or PR to the date of objective progression or the date of death due to any cause, whichever is earlier.

**DCR:** the percentage of patients with a BOR of CR, MR, PR, or SD.

**CBR:** the percentage of patients with a BOR of CR, MR, PR, or SD for at least 6 months.

**Investigator assessed PFS:** the time from first dose of any drug in study treatment to documented disease progression per INRC or death, whichever occurs first. The Kaplan-Meier method (Kaplan and Meier 1958) will be used to estimate the PFS curves as well as PFS rates at appropriate time intervals (for example, at 3 and 6 months). Detailed censoring rules are provided in Table JPCS.7.3.

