Serum or urine pregnancy test	X			X			X			X			X			
For women of childbearing potential only. See Section 8.3.4 and Section 10.2, Appendix 2. Note: during study treatment, perform at start of each cycle (≤ 3 days) or as required per local regulations and/or institutional guidelines.

Parts A and B															
Procedure	All Treatment Periods (Cycle = 21 Days)														Notes
	Cycle 1			Cycle 2			Cycle 3			Cycle 4			Cycle 5-n		
Relative Day within Dosing Cycle	1	8	15	1	8	15	1	8	15	1	8	15	1	8	15
Radiologic imaging	See Notes														Scans will be performed and reviewed locally, 
 • Scan after Cycle 2 (prior to administering study drug for C3D1) • after Cycle 4 (prior to administering study drug for C5D1) • the end of every third cycle thereafter (after Cycle 7 [prior to administering study drug for C8D1], after Cycle 10 [prior to administering study drug for C11D1], etc.) Completion up to 7 days before Day 1 of each cycle with imaging is acceptable. RECIST v1.1 should be used for all non-CNS tumors; RANO criteria should be used for CNS tumors. For patients with non-CNS tumors, perform a CT scan of the known lesion(s) and of the chest. For CNS tumors, perform MRI of the primary lesion including the entire brain or spine as applicable. For brain lesions, also include MRI of the spine if history of drop metastases or if new drop metastases were present at baseline scan. If images of bones are present in the above scans, bones should be assessed for gross bone abnormalities. For patients unable to adhere to this schedule due to exceptional circumstances, the investigator should consult with the Lilly CRP/CRS. Imaging facility, image acquisition protocol, and imaging modality should be consistent for all visits for a given patient.

Parts A and B															
Procedure	All Treatment Periods (Cycle = 21 Days)														Notes
	Cycle 1			Cycle 2			Cycle 3			Cycle 4			Cycle 5-n		
Relative Day within Dosing Cycle	1	8	15	1	8	15	1	8	15	1	8	15	1	8	15
Lumbar puncture	See Notes														Assess CSF cytology and tumor markers (alpha-fetoprotein and beta-HCG) according to institutional/standard guidelines for applicable patients who had positive tumor markers or cytology at baseline.
AE Collection / CTCAE Grading	See Notes														AEs collected continuously throughout study (any time there is an AE to report). CTCAE Version 5.0.

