Tumor evaluation: CT or MRI		End of Cycles 2, 4, and 6, then at the end every 4th cycle	
 Up to 1 week prior to the start of the next planned cycle of therapy Repeat assessment ≥4 weeks after initial response for patients with complete response, partial response, and minor response Use same modality throughout the study Scans will be performed and reviewed locally
Tumor evaluation: MIBG or PET CT		End of Cycles 2, 4, and 6, then at the end every 4th cycle	
 Up to 1 week prior to the start of the next planned cycle of therapy PET CT only for patients with non-MIBG avid lesions Repeat assessment ≥4 weeks after initial response for patients with complete response, partial response, and minor response Scans will be performed and reviewed locally
Bilateral bone marrow aspirates/biopsies		End of Cycles 2, 4, 6 and then after every 4th cycle - only for patients with marrow disease and all patients (even if no marrow disease) following Cycle 6	Up to 1 week prior to the start of the next planned cycle of therapy
Biomarkers – plasma	X	X	
 Collect pre-dose at C1D1 on participants CCI only Collect at disease progression and/or study discontinuation on participants CCI
Biomarkers - whole blood	X		
 For participants CCI whole blood dried blood spot For participants CCI whole blood sample If not collected during screening/baseline, then obtain at C1D1 If blood volume restrictions prevent collection during screening/baseline and C1D1, then sample can be collected at a subsequent timepoint

Part C			
Procedures	During Cycle 1	Cycle 2 onward	Instructions
			
 Only one sample is needed per patient See Section 8.8
Drug product acceptability and palatability questionnaire	Days 1 and 15	Cycle 2 Day 1 only	
 For patients \leq5 years old, only the caregiver will complete For patients \geq6 to $<$12 years old, patient and caregiver will complete For patients \geq12 years old, only the patient will complete Perform at time of dosing or within approximately 30 minutes after dose If method of abemaciclib administration or formulation (tablets to granules or vice versa) changes, the appropriate questionnaire corresponding to the new administration method and formulation should be completed at the clinic visit following this change

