Part A will be executed first to confirm the MTD of abemaciclib in combination with irinotecan and temozolomide. The MTD is defined as the highest dose level at which less than 33% of patients experience a DLT during Cycle 1. After the MTD of abemaciclib in Part A has been determined, Parts B and C will open. As Part B reduces cumulative exposure to myelosuppressive agents, it will enroll at a starting dose one level higher than the abemaciclib MTD in Part A (not to exceed 115 mg/m $^2$ ). Since Part B will not start at the lowest dose level (unless the lowest dose level of Part A is not tolerated), this sequential design has potential to minimize the number of patients necessary to complete Part B. The dose escalation/de-escalation method for abemaciclib in Parts A and B is described in detail in Section 6.1.1. Part C will utilize the MTD for the combination of abemaciclib, irinotecan, and temozolomide identified in Part A and the standard dosing of dinutuximab and GM-CSF (Mody et al. 2020) as the starting dose. Part C consists of 2 stages that will evaluate (1) safety and tolerability and (2) anti-tumor activity of the combination (details in Section 6.1.2).

DLTs will be evaluated during the 21 days of treatment in Cycle 1. After the MTD has been identified, an expansion cohort for each part will be enrolled to further inform safety and PK and to confirm the tolerability in additional patients.

The cycle length is 21 days. Patients will continue study treatment until at least one of the discontinuation criteria is met (Protocol Section 7). Continuation on chemotherapy beyond Cycle 12 will be up to the investigator's discretion and the individual patient's situation. Prior to

continuing the patient on chemotherapy beyond Cycle 12, the investigator should discuss with the Lilly clinical research physician/clinical research scientist (CRP/CRS).

The primary objective in Parts A and B is to determine the RP2D of **abemaciclib in combination with irinotecan and temozolomide (Part A)**, and **abemaciclib in combination with temozolomide (Part B)** in patients with relapsed/refractory solid tumors. The secondary objectives include the assessment of the safety profile, preliminary anti-tumor activity, and abemaciclib acceptability and palatability. **CCI**

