### **7.1.2. Definitions and Conventions**

Study drug refers to abemaciclib.

Study treatment refers to abemaciclib plus irinotecan and temozolomide for patients in Part A, abemaciclib plus temozolomide for patients in Part B, and abemaciclib plus dinutuximab, GM-CSF, irinotecan, and temozolomide in Part C.

Date of first dose is the date of the first dose of study drug, irinotecan, temozolomide, dinutuximab, or GM-CSF.

Study day will be calculated as the difference between the date of the event or assessment and:

- The date of first dose plus 1 for all events or assessments occurring on or after the day of first dose. For example, if an event occurs on 08 November 2020 and the date of first dose was 06 November 2020, the study day of the event is 3.
- The date of first dose for all events or assessments occurring before the day of first dose. For example, if an event occurs on 05 November 020 and the date of first dose was 06 November 2020, the study day of the event is -1.

One month is defined as 365/12 days.

Unless otherwise noted, summaries of continuous variables will include a mean, median, standard deviation, minimum, and maximum.

Unless otherwise noted, summaries of categorical variables will include the frequency and percentage (relative to the population being analyzed) of each category.

The assumptions for each statistical method will be evaluated. If there is violation of assumptions, alternative statistical methods may be used. Additional exploratory analyses of the data will be conducted as deemed appropriate. Unless otherwise stated, all tests of treatment effects will be conducted at a 1-sided alpha level of .025, and all CIs will be given at a 2-sided 95% level.

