**Table JPCS.7.3. JPCS PFS Censoring Scheme**

Situation a	Event/Censor	Date of Event or Censor
Tumor progression or death	Event	Earliest date of PD or death
No tumor progression and no death	Censored	Date of last adequate assessment or date of first dose (whichever is later) b
Unless		
No adequate baseline tumor assessment available	Censored	Date of first dose
No adequate postbaseline tumor assessment available and death reported after 2 scan intervals after first dose	Censored	Date of first dose
New anticancer treatment started and no tumor progression or death within 14 days	Censored	Date of adequate assessment prior to (start of new therapy +14 days) or date of first dose (whichever is later)
Tumor progression or death documented immediately after 2 or more scan intervals after last adequate tumor assessment or first dose (whichever is later) b	Censored	Date of last adequate assessment or date of first dose (whichever is later) b

Abbreviations: CR = complete response; MR = minimal response; PD = progressive disease; PFS = progression-free survival; PR = partial response; SD = stable disease.

a Symptomatic deterioration (that is, symptomatic progression that is not radiologically confirmed) will not be considered as tumor progression.

b Adequate tumor assessment refers to an assessment with one of the following responses: CR, PR, MR, SD, or PD.

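### Part C has no routine on-treatment scan between Day 126 and Day 203, so its 6-month Kaplan-Meier PFS rate is biased upward, and the stable-disease part of the CBR lacks a duration rule

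*SAP*

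**What the plan says.** For Part C, SAP 7.3.2.2 plans Kaplan-Meier estimates of "PFS rates at appropriate time intervals (for example, at 3 and 6 months". It defines the CBR as "the percentage of patients with a BOR of CR, MR, PR, or SD for at least 6 months". SAP 7.3.2.1 gives Parts A and B a CBR in which CR and PR count outright and only SD carries the 6-month condition. I read the Part C wording the same way, with MR added.

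The time scale is fixed in SAP 7.1.2: "One month is defined as 365/12 days". SAP 6.1 adds: "The cycle length is 21 days".

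The Part C on-treatment schedule (Protocol 1.3.2) places both CT/MRI and MIBG/PET at "End of Cycles 2, 4, and 6, then at the end every 4th cycle", with a window of "Up to 1 week prior to the start of the next planned cycle of therapy". In Parts A and B (Protocol 1.3.1) scans follow Cycles 2 and 4 and then come at "the end of every third cycle thereafter", so after Cycles 7 and 10.

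SAP Table JPCS.7.3 dates a PFS event at the earlier of PD and death. Its footnote a rules out clinical worsening alone: "symptomatic progression that is not radiologically confirmed) will not be considered as tumor progression".

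Neither document says whether the duration of SD ends at the PD date or at the last assessment without PD.

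**The concern.** The SAP names a landmark at which the Part C schedule takes no routine measurement. A tumour that starts to grow on, say, Day 130 in a patient who stays on treatment would normally be found at the Cycle 10 scan and dated there. That patient is then progression-free at 6 months in the Kaplan-Meier curve.

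PFS and the CBR are the secondary endpoints that describe how long activity lasts. Part C has a single arm, so no concurrent control shares the error, and readers may set the figures beside outside rates such as the backbone's one-year PFS in Protocol 2.2. The confidence interval around a Kaplan-Meier rate does not allow for an error in event dating.

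For the CBR the stake is different. An open-label study would be choosing, after the data are known, a convention that moves a listed secondary endpoint up or down.

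**Working it through.** The plan states no scan times in months, so there is no figure of its own to reproduce.

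**Inputs from the documents.** Month of 365/12 days; cycle of 21 days; scan schedule and 7-day backward window; backbone one-year PFS of 67.9% (Protocol 2.2), used only to size the effect; 46 patients at the RP2D (SAP 6.3).

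**Assumptions.** Exponential PFS, cycles on time, and medians of 12 and 6 months as alternatives to the quoted rate.

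**Scan days.** Six months is 6 × 365/12 = 182.5 days. Scan day is 21 × cycle number, less 0 to 7 days.

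- Part C, end of Cycle 6: 21 × 6 = 126, so Day 119-126 (3.91-4.14 months), 56.5 to 63.5 days before the landmark.
- Part C, end of Cycle 10: 21 × 10 = 210, so Day 203-210 (6.67-6.90 months), 20.5 to 27.5 days after it.
- Parts A/B, end of Cycle 7: 21 × 7 = 147, so Day 140-147 (4.60-4.83 months). The next scan is again Day 203-210.

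The 3-month landmark (Day 91.25) is little affected, since a scan falls at Day 77-84.

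**Part C PFS at 6 months.** Let S(t) = exp(-ht). If every event in the gap is found and dated at the Cycle 10 scan, Kaplan-Meier at Day 182.5 returns S(126), and the bias is S(126) - S(182.5). At the quoted rate, h = -ln(0.679)/365 = 0.00106 per day.

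| PFS assumption | S(182.5) | S(126) | Bias (points) | Bias if half of gap events keep their own date |
|---|---|---|---|---|
| One-year PFS 67.9% | 0.824 | 0.875 | +5.1 | +2.5 |
| Median 12 months | 0.707 | 0.787 | +8.0 | +4.0 |
| Median 6 months | 0.500 | 0.620 | +12.0 | +6.0 |

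At the early edge of the window (Day 119) the first bias becomes +5.7. The last column multiplies by (1 - f), where f = 0.5 is the share of gap events that are deaths or PD imaged between routine scans.

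For scale, the binomial standard error with 46 patients is √(0.824 × 0.176/46) = 5.6 points, or √(0.707 × 0.293/46) = 6.7 points. The unreduced bias in the first two rows is about one standard error.

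**CBR, SD component.** There are two possible rules.

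- SD ends at the PD date. Progression in the gap is dated Day 203-210, so SD exceeds 182.5 days. In Part C the modelled error is that of the table. In Parts A/B, with the scan on Day 147, it is +4.9 to +7.9 points for medians of 2 to 12 months.
- SD ends at the last non-PD scan. The patient needs the Day 203-210 scan, and the error is S(203 to 210) - S(182.5). At 67.9% this is 0.806 to 0.800 against 0.824, or -1.8 to -2.4 points. For medians of 2 to 12 months it is -2.6 to -5.1. This applies in all parts.

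These errors apply to patients whose best response is SD. The shift in the CBR itself is smaller, in proportion to their share of the cohort.

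**The case against.** The strongest reply is that the sizes above are ceilings and that little depends on them. Several provisions bring information into the gap.

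- Deaths keep their own dates.
- Protocol 1.3.2 asks responders for a repeat assessment four or more weeks after first response, so a response first seen on Day 126 brings imaging from Day 154.
- Patients who stop treatment without PD are restaged at the 30-day visit and then at 90-day visits. One who stops near Day 130 would be imaged around Day 160.
- Protocol 6.5.1 makes deterioration that needs other systemic anticancer therapy a reason to stop study treatment. If a new therapy starts and no PD or death occurs within 14 days, Table JPCS.7.3 censors the patient at an earlier assessment, so the patient is not carried event-free past 6 months.

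All of this stands. A reader might infer that the 6-month PFS rate is merely Cycle 6 status under another name. The documents do not support that. The bias is confined to progression in patients who stay on treatment and are not imaged off schedule.

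A reader might also suppose that cycle delays make matters worse. Delays before the Cycle 6 scan move it towards Day 182.5 (56.5 days of cumulative delay would put it there), and later delays do not change the last scan before the landmark.

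It is also fair that 3 and 6 months are only examples, that the analyses are mainly descriptive, and that the Part C decision rests on ORR. This lowers the stakes and makes the change easy, but it does not remove the bias if 6 months is reported. The outside study's PFS may carry a similar error, but its scan schedule is not in the documents, so the two cannot be assumed to cancel.

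**Conclusion.** The point holds for Part C PFS. The 6-month Kaplan-Meier rate is biased upward, by at most about 5 points at the quoted one-year PFS with nominal scan timing, and by about 8 at an assumed 12-month median. Both figures rest on exponential PFS and on every event being found at a routine scan. The provisions listed above reduce them, and shorter medians would raise them.

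For the CBR, the supportable finding is a missing rule. A reader might infer that the CBR is overstated, or that the error always favours the combination. That follows only if SD runs to the PD date. If SD runs to the last non-PD scan, the SD component is understated by about 2 to 5 points.

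A reader might also extend the PFS point to Parts A and B. Protocol 9.4.6.1 mentions 6-month PFS there, but the objectives table lists PFS for Part C only and SAP 7.3.2.1 omits it, so only the CBR rule matters in those parts.

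This is a secondary-endpoint estimation issue. The primary ORR and the two-stage decision are untouched.

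**What to change.** In SAP 7.3.2.2, do one of the following for Part C PFS:

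- replace the 6-month example with landmarks tied to the scans, for example 18 and 30 weeks (Days 126 and 210), read after the scan window has closed; or
- keep 6 months and give an interval-censored estimate beside Kaplan-Meier. Name the estimator: with few assessments inside the gap, a nonparametric one mainly bounds the Day 182.5 value, so any interpolation is an assumption to state.

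For the CBR in all parts (SAP 7.3.2.1 and 7.3.2.2), state when SD ends. If the rule is a non-PD assessment on or after Day 183, note that in practice this means the Day 203-210 scan and is modestly conservative.

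Add no PFS landmarks for Parts A and B.

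The cost is SAP wording and minor programming, with no extra scans. The downside is slightly less favourable durability figures.

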**Table JPCS.7.3. JPCS PFS Censoring Scheme**

Situation a	Event/Censor	Date of Event or Censor
Tumor progression or death	Event	Earliest date of PD or death
No tumor progression and no death	Censored	Date of last adequate assessment or date of first dose (whichever is later) b
Unless		
No adequate baseline tumor assessment available	Censored	Date of first dose
No adequate postbaseline tumor assessment available and death reported after 2 scan intervals after first dose	Censored	Date of first dose
New anticancer treatment started and no tumor progression or death within 14 days	Censored	Date of adequate assessment prior to (start of new therapy +14 days) or date of first dose (whichever is later)
Tumor progression or death documented immediately after 2 or more scan intervals after last adequate tumor assessment or first dose (whichever is later) b	Censored	Date of last adequate assessment or date of first dose (whichever is later) b

Abbreviations: CR = complete response; MR = minimal response; PD = progressive disease; PFS = progression-free survival; PR = partial response; SD = stable disease.

a Symptomatic deterioration (that is, symptomatic progression that is not radiologically confirmed) will not be considered as tumor progression.

b Adequate tumor assessment refers to an assessment with one of the following responses: CR, PR, MR, SD, or PD.

### 7.3.3. *Exploratory Efficacy Endpoints*

CCI  
CCI

CCI  
CCI

CCI

## 7.4. Other Statistical Analyses

### 7.4.1. Patient Disposition

The number and percentage of patients entered into the study and treated, as well as reasons for discontinuation from study treatment and reasons for discontinuation from study, will be summarized by treatment arm or cohort. The numbers and percentages of patients completing the study (completed at least 1 cycle of treatment) will also be summarized. A listing of patient disposition will be provided.

